4.5.1.6 Continuing Nivolumab with Suspected Progression

Accumulating evidence indicates that a minority of subjects treated with immunotherapy may derive clinical benefit despite initial evidence of disease progression, eg, due to inflammatory reaction simulating progression (“tumor flare” or pseudoprogression). Subjects on the RT + nivolumab arm may, at investigator discretion, continue nivolumab in the setting of suspected progression until progression is confirmed. [Note: this is not the same as confirmation of progression occurring within 12 weeks after RT, which applies to both treatment arms.] Communication with the BMS Medical Monitor is strongly encouraged. If the investigator believes that the subject continues to derive clinical benefit by continuing treatment, the subject should continue assessments according to [Table 5.1-2](#).

Subjects may continue nivolumab beyond initial (suspected) progression only if they meet the following criteria:

- Subject is tolerating nivolumab

- Treatment will not delay intervention to prevent imminent complications, eg surgery for relief of symptomatic intracranial mass effect
- Investigator-assessed overall clinical benefit

Radiographic assessment should be repeated after suspected progression as clinically required in order to determine whether there has been a decrease in the tumor size or continued progression. If possible, perfusion images should also be obtained. All MRI scans should be submitted to the imaging vendor as soon as possible.

Re-operation should be considered, if lesion is surgically accessible, to differentiate immune-treatment effects from progression. The BMS Medical Monitor should be consulted. Potential for clinical benefit should be balanced by clinical judgment as to whether the subject is clinically deteriorating and unlikely to receive benefit from continued treatment with nivolumab. Nivolumab treatment should be discontinued permanently upon confirmation of RANO-assessed progression but prolonged observation (eg, 3 months) may be required, as suggested in Okada et al.⁴⁰

4.5.1.7 Management Algorithms for Immuno-Oncology Agents

Immuno-oncology (I-O) agents are associated with AEs that can differ in severity and duration than AEs caused by other therapeutic classes. Nivolumab is considered an immuno-oncology agent in this protocol. Early recognition and management of AEs associated with immuno oncology agents may mitigate severe toxicity. Management Algorithms have been developed to assist investigators in assessing and managing the following groups of AEs:

- Gastrointestinal
- Renal
- Pulmonary
- Hepatic
- Endocrinopathy
- Skin
- Neurological

The above algorithms are found in [Appendix 1](#) and in the nivolumab Investigator Brochure.

4.5.1.8 Treatment of Nivolumab-Related Infusion Reactions

Since nivolumab contains only human immunoglobulin protein sequences, it is unlikely to be immunogenic and induce infusion or hypersensitivity reactions. However, if such a reaction were to occur, it might manifest with fever, chills, rigors, headache, rash, pruritus, arthralgias, hypotension, hypertension, bronchospasm, or other allergic-like reactions. All Grade 3 or 4 infusion reactions should be reported within 24 hours to the study medical monitor and reported as an SAE if it meets the criteria. Infusion reactions should be graded according to NCI CTCAE (Version 4.03) guidelines.

Treatment recommendations are provided below and may be modified based on local treatment standards and guidelines, as appropriate:

For **Grade 1** symptoms: (mild reaction; infusion interruption not indicated; intervention not indicated):

- Remain at bedside and monitor subject until recovery from symptoms. The following prophylactic premedications are recommended for future infusions: diphenhydramine 50 mg (or equivalent) and/or acetaminophen/paracetamol 325 to 1000 mg at least 30 minutes before additional nivolumab administrations.

For **Grade 2** symptoms: (moderate reaction required therapy or infusion interruption but responds promptly to symptomatic treatment (eg, antihistamines, non-steroidal anti-inflammatory drugs, narcotics, corticosteroids, bronchodilators, IV fluids); prophylactic medications indicated for \leq 24 hours):

- Stop the nivolumab infusion, begin an IV infusion of normal saline, and treat the subject with diphenhydramine 50 mg IV (or equivalent) and/or acetaminophen/paracetamol 325 to 1000 mg; remain at bedside and monitor subject until resolution of symptoms. Corticosteroid and/or bronchodilator therapy may also be administered as appropriate. If the infusion is interrupted, then restart the infusion at 50% of the original infusion rate when symptoms resolve; if no further complications ensue after 30 minutes, the rate may be increased to 100% of the original infusion rate. Monitor subject closely. If symptoms recur, then no further BMS-936558 will be administered at that visit.
- For future infusions, the following prophylactic premedications are recommended: diphenhydramine 50 mg (or equivalent) and/or acetaminophen/paracetamol 325 to 1000 mg should be administered at least 30 minutes before nivolumab infusions. If necessary, corticosteroids (up to 25 mg of SoluCortef or equivalent) may be used.

For **Grade 3 or 4** symptoms: (severe reaction, Grade 3: prolonged [ie, not rapidly responsive to symptomatic medication and/or brief interruption of infusion]; recurrence of symptoms following initial improvement; hospitalization indicated for other clinical sequelae (eg, renal impairment, pulmonary infiltrates). Grade 4: Life threatening; pressor or ventilatory support indicated):

- Immediately discontinue infusion of nivolumab. Begin an IV infusion of normal saline and treat the subject as follows: Recommend bronchodilators, epinephrine 0.2 to 1 mg of a 1:1000 solution for subcutaneous administration or 0.1 to 0.25 mg of a 1:10,000 solution injected slowly for IV administration, and/or diphenhydramine 50 mg IV with methylprednisolone 100 mg IV (or equivalent), as needed. Subject should be monitored until the Investigator is comfortable that the symptoms will not recur. Nivolumab will be permanently discontinued. Investigators should follow their institutional guidelines for the treatment of anaphylaxis. Remain at bedside and monitor subject until recovery of the symptoms.

In case of late-occurring hypersensitivity symptoms (eg, appearance of a localized or generalized pruritus within 1 week after treatment), symptomatic treatment may be given (eg, oral antihistamine or corticosteroids).

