4.5.1.5 Treatment Discontinuation Criteria for Nivolumab

Nivolumab treatment should be permanently discontinued for the following:

- Any Grade 2 drug-related uveitis, eye pain or blurred vision that does not respond to topical therapy and does not improve to Grade 1 severity within the re-treatment period OR requires systemic treatment.
- Any Grade 3 non-skin, drug-related AE lasting > 7 days or recurs, with the following exceptions for laboratory abnormalities, drug-related uveitis, pneumonitis, bronchospasm, neurological toxicity, hypersensitivity reactions, infusion reactions, and endocrinopathies:
 - Grade 3 drug-related uveitis, pneumonitis, bronchospasm, neurological toxicity, hypersensitivity reaction, or infusion reaction of any duration requires discontinuation
 - Grade 3 drug-related endocrinopathies adequately controlled with only physiologic hormone replacement do not require discontinuation. Adrenal insufficiency requires discontinuation regardless of control with hormone replacement.
 - Grade 3 drug-related laboratory abnormalities do not require treatment discontinuation except:
 - ◆ Grade 3 drug-related thrombocytopenia > 7 days or associated with bleeding requires discontinuation
 - ◆ Grade ≥ 3 drug-related AST, ALT, or total bilirubin requires discontinuation*
*In most cases of Grade 3 AST or ALT elevation, study drug(s) will be permanently discontinued. If the investigator determines a possible favorable benefit/risk ratio that warrants continuation of study drug(s), a discussion between the investigator and the BMS Medical Monitor/designee must occur.
 - ◆ Concurrent AST or ALT > 3 x ULN and total bilirubin > 2 x ULN

- Any Grade 4 drug-related AE or laboratory abnormality (including but not limited to creatinine, AST, ALT, or total bilirubin), except for the following events which do not require discontinuation:
 - Grade 4 neutropenia \leq 7 days
 - Grade 4 lymphopenia or leukopenia or asymptomatic amylase or lipase
 - Isolated Grade 4 electrolyte imbalances/abnormalities that are not associated with clinical sequelae and are corrected with supplementation/appropriate management within 72 hours of their onset.

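### Protocol sections 4.5.1.8 and 4.5.1.5 are not reconciled for a nivolumab infusion reaction that recurs after the infusion is restarted

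*Protocol*

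**What the plan says.** Protocol section 4.5.1.8 sets out the management of nivolumab infusion reactions in three blocks: Grade 1, Grade 2, and Grade 3 or 4.

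- **Grade 2, restart.** The infusion is stopped and symptoms are treated. Then: "If the infusion is interrupted, then restart the infusion at 50% of the original infusion rate when symptoms resolve".
- **Grade 2, recurrence.** "If symptoms recur, then no further BMS-936558 will be administered at that visit".
- **Grade 2, later doses.** The following bullet begins "For future infusions, the following prophylactic premedications are recommended". It makes no exception for subjects whose symptoms came back.
- **Grade 3 or 4, definition.** The text introducing this block includes, for Grade 3, "recurrence of symptoms following initial improvement; hospitalization indicated for other clinical sequelae".
- **Grade 3 or 4, action.** The bullet under it states "Nivolumab will be permanently discontinued".
- **Reporting.** The opening paragraph states "All Grade 3 or 4 infusion reactions should be reported within 24 hours to the study medical monitor". It sets no such deadline for Grade 2.

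Section 4.5.1.5 separately says that a Grade 3 drug-related "hypersensitivity reaction, or infusion reaction of any duration requires discontinuation". Section 3.5 makes toxicity under 4.5.1.5 a reason for which investigational product must be stopped.

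Two further sentences in 4.5.1.8 bear on the question. One says that infusion reactions are graded by CTCAE version 4.03. The other introduces the graded blocks as recommendations that sites may adapt to local standards.

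**The concern.** A recurrence after restart is dealt with inside the Grade 2 block, yet the protocol's own Grade 3 wording also describes it. The two blocks differ in what happens after that visit and in what must be reported.

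A site that follows the Grade 2 text literally could give the next scheduled dose with premedication. A site that applies the Grade 3 descriptor would stop nivolumab permanently and notify the medical monitor within 24 hours. Each could point to protocol text. At stake are a re-exposure decision after a repeat reaction, prompt reporting, and consistent safety data. The SAP tabulates reasons for discontinuing treatment (7.3.1), AEs leading to discontinuation (7.1.1), nivolumab doses received (7.4.1), and infusion interruptions with their reasons (7.4.2.2). Some of these could record the same event differently from site to site.

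**Working it through.** The plan states no figure on this point, so the check is a comparison of texts. Take one subject: a Grade 2 reaction occurs, the infusion is stopped, symptoms resolve, the infusion restarts at half rate, and symptoms return.

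| Question | Grade 2 block, 4.5.1.8 | Grade 3 or 4 block, 4.5.1.8, with 4.5.1.5 |
|---|---|---|
| Does the text describe the event? | Yes: it has an explicit recurrence sentence | Yes: "recurrence of symptoms following initial improvement" is a listed Grade 3 feature |
| Rest of that visit | No more nivolumab | No more nivolumab |
| Later visits | Left open, with premedication advice and no exclusion | Permanent discontinuation |
| Medical monitor within 24 hours | Not stated | Required |

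1. **Overlap.** Symptoms that resolved, allowed a restart and then returned have recurred after initial improvement. The event meets both descriptions without straining either.
2. **Where the texts agree.** At the visit itself both stop the infusion.
3. **Where they diverge.** They part at the next dose and at the reporting duty. The Grade 2 recurrence sentence is tied to that visit and is followed by advice for later infusions. The Grade 3 text, and 4.5.1.5 through section 3.5, end treatment.
4. **Does the grading instruction decide?** It says which scale to use. It does not say whether the Grade 2 recurrence sentence still applies once symptoms have returned. If every such recurrence is to be Grade 3, the Grade 2 block should send the reader there; instead it keeps a rule of its own.
5. **Does the local-modification sentence decide?** It covers the recommendations in 4.5.1.8. Section 4.5.1.5 has no equivalent sentence, and local discretion does not settle the grade or the reporting duty.

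**The case against.** The best defence is that the two texts can be obeyed in sequence. The Grade 2 sentence is a same-day instruction, and a permanent stop also satisfies it. The investigator stops the infusion, grades the recurrence by CTCAE, and lets the assigned grade select the block. Once the event is Grade 3, 4.5.1.5 gives a single instruction. The premedication bullet addresses Grade 2 reactions generally and does not direct that a subject with a recurrence be treated again.

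Much of this stands, and it rules out stronger readings that a reader might infer:

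- **That the rules are flatly opposite.** They are not. The Grade 2 text never says that the stop is limited to that visit; this follows only from its wording taken together with the bullet on later infusions.
- **That the protocol has nothing on how to choose a block.** It does name a grading standard.
- **That safety-table grades are set by these management blocks.** SAP section 7.1.1 grades severity by CTCAE. Any variation between sites would come through investigators' grading, and the documents give no basis for sizing it.

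What the defence does not supply is the missing link. The act-then-regrade sequence is reasonable but unwritten. The recurrence rule sits inside the Grade 2 block, so a literal reader could re-expose a subject for whom 4.5.1.5 requires discontinuation.

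**Conclusion.** The point holds as an unreconciled overlap within 4.5.1.8, and between its Grade 2 block and 4.5.1.5. It affects the action at later doses and the 24-hour report.

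The size cannot be taken from the documents, which give no incidence of infusion reactions or of recurrence. With 550 / 2 = 275 subjects planned for nivolumab, a reader might assume any-grade reactions in 1% to 10% and recurrence in 10% to 30% of those. That gives 275 × 0.01 × 0.10 = 0.3 to 275 × 0.10 × 0.30 = 8.3 subjects. Both rates are pure assumptions and the base is too wide: under 4.5.1.8 a restart follows only an interrupted Grade 2 infusion. On these rates the figures overstate the number, so they support no more than that few subjects, possibly none, are likely to be affected.

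The OS analysis is unaffected: it compares all randomized subjects as randomized, and no sample-size or alpha figure depends on this text. The point deserves correction because each case is a re-exposure decision and the correction is small. Nothing here implies which action is clinically right.

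**What to change.** Reconcile three texts: the Grade 2 recurrence sentence and the Grade 3 descriptor in 4.5.1.8, and the infusion-reaction line in 4.5.1.5. Recurrence after restart should have one grade, one action and one reporting rule, consistent with the CTCAE grading that the protocol names. A cross-reference in the Grade 2 bullet, naming the block that applies once symptoms recur, would be enough. The sponsor's clinicians should decide the action.

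For recurrences already recorded, query the site to confirm the CTCAE grade and whether the required report was made. Do not regrade them by a newly written protocol rule, since the protocol and the SAP both make CTCAE the grading standard.

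The cost is about one sentence, in the next amendment or in an administrative letter if the sponsor regards it as a clarification, plus a query for each recorded recurrence.

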4.5.2 Temozolomide Dosing

4.5.2.1 Temozolomide Dose and Schedule

Subjects on RT + TMZ will be administered temozolomide (TMZ, Temodar[®]) daily during RT and as maintenance therapy for 6 cycles. TMZ dosing will be performed according to institutional standard; the following guidance is drawn from published literature.

Temozolomide (TMZ) will be dosed at 75 mg/m² once per day continuously throughout RT, typically for 42 days and with a maximum of 49 days. See [Table 4.5.2.3-1](#) for dose modifications during concomitant RT + TMZ dosing. After completion of RT, there will be a 4-week break. Subjects will receive 6 cycles of temozolomide daily x 5 days every 28 days.

Dose Level	TMZ Dose in mg/m²/day	Notes
-1	100 mg/m ² /day	Reduction for prior toxicity
0	150 mg/m ² /day	Dose during Cycle 1
1	200 mg/m ² /day	Dose during C2-6 in absence of TMZ-related toxicity

Source: adapted from Temodar[®] package insert (PI)

In the first maintenance cycle TMZ is given at a dose of 150 mg/m², and then increased to 200 mg/m² in cycle 2 as follows: If, during the first cycle, all non-hematologic AEs observed were grade ≤ 2 (except alopecia, nausea and vomiting) and with platelets ≥ 100 x 10⁹/L and ANC ≥ 1.5 x 10⁹/L, then the temozolomide dose should be escalated to dose level 1 and this dose should be used as the starting dose for subsequent cycles. Doses of TMZ are not precise but are adjusted based on tolerance; rounding of up to 10% is entirely acceptable.

If treatment after cycle 1 has to be delayed because of ongoing non-hematologic AEs of grade ≥ 2, then no escalation is possible. If the dose was not escalated at Cycle 2, then the dose should not be escalated in further cycles based on AEs (see [Table 4.5.2.3-2](#)). If there was a prior dose reduction during the concomitant period with RT, then dose -1 should be the starting dose for subsequent cycles. Table 4.5.2.1-1 describes dose levels during temozolomide monotherapy.

4.5.2.2 Criteria to Start Temozolomide Maintenance Cycles

Maintenance treatment begins following a 4 week treatment break after RT. TMZ treatment may begin if blood count (obtained within the prior 3 days) shows ANC ≥ 1.5 x 10⁹/L, platelet count ≥ 100 x 10⁹/L and any Grade ≥ 3 non-hematologic AE (except alopecia) must have resolved to grade ≤ 1). If AEs persist, treatment should be delayed by 1 week for up to 4 consecutive weeks.

If, after 4 weeks of delay, all AEs have still not resolved to \leq grade 1: then any further maintenance treatment with temozolomide should be discontinued.

4.5.2.3 Dose Modifications or Discontinuation for Temozolomide

Table 4.5.2.3-1: Temozolomide Dose Modification Guidelines During Concomitant Radiotherapy and TMZ Dosing		
Laboratory Value/Clinical Criteria:	Dose Modification	Additional Information:
ANC:		
≥ 0.5 and $< 1.5 \times 10^9/L$	Delay TMZ Dosing	Continue when $\geq 1.5 \times 10^9/L$
$< 0.5 \times 10^9/L$	Discontinue TMZ	May restart at dose -1 in maintenance
Platelets:		
≥ 10 and $< 100 \times 10^9/L$	Delay TMZ Dosing	Continue when $\geq 100 \times 10^9/L$
$< 10 \times 10^9/L$	Discontinue TMZ	May restart at dose -1 in maintenance
Any Non-Hematologic Toxicity (except alopecia, nausea, vomiting)		
CTC Grade 2	Delay TMZ dosing	Continue when \leq CTC Grade 1 (except for alopecia, nausea, vomiting)
CTC Grade 3 or 4	Discontinue TMZ dosing	May restart at dose -1 in maintenance

Source: adapted from Temodar® package insert (PI)

Table 4.5.2.3-2: Temozolomide Dose Modification Guidelines During Maintenance TMZ Dosing		
Laboratory Value/Clinical Criteria:	Dose Modification^a	Additional Information:
ANC:		
$< 1.0 \times 10^9/L$	Reduce TMZ Dosing by 1 dose level per Table 5.4.2-1	
$< 0.5 \times 10^9/L$	Discontinue TMZ dosing	If Dose Level -1 (100 mg/m ²) still results in unacceptable toxicity
Platelets:		
≥ 10 and $< 100 \times 10^9/L$	Reduce TMZ Dosing by 1 dose level per Table 5.4.2-1	
$< 10 \times 10^9/L$	Discontinue TMZ dosing	If Dose Level -1 (100 mg/m ²) still results in unacceptable toxicity

Table 4.5.2.3-2: Temozolomide Dose Modification Guidelines During Maintenance TMZ Dosing		
Laboratory Value/Clinical Criteria:	Dose Modification^a	Additional Information:
Any Non-Hematologic Toxicity (except alopecia, nausea, vomiting)		
CTC Grade 3	Reduce TMZ Dosing by 1 dose level per Table 5.4.2-1	
CTC Grade 4	Discontinue TMZ dosing	If Dose Level -1 (100 mg/m ²) still results in unacceptable toxicity or the same Grade 3 non-hematologic toxicity recurs

^a Dose reductions of temozolomide during maintenance should be based on the on the lowest blood count and worst non-hematologic toxicity during the prior cycle.

Source: adapted from Temodar® package insert (PI)

4.5.2.4 Supportive Care during Temozolomide

Subjects should be treated receive prophylaxis against *Pneumocystis pneumonia* (inhaled pentamidine [preferred], dapsone or oral trimethoprim–sulfamethoxazole) during concomitant treatment with RT plus TMZ and may be continued during maintenance at investigator discretion. Details regarding prophylactic agent use will be collected as concomitant medications.

Antiemetic prophylaxis with metoclopramide or a 5-hydroxytryptamine 3 antagonist is allowed prior to treatment with temozolomide.

4.6 Blinding/Unblinding

Not applicable.

4.7 Treatment Compliance

Assessment of study medications will be performed at each study visit. For subjects receiving temozolomide, the subject should be instructed to bring all unused study drug to each visit as well as any empty containers. The dates and number of capsules dispensed and returned must be recorded on the drug accountability form maintained on-site. Unused or partially used study drug are returned to the subject and dosing should continue from the in-use container until it has been emptied. Subjects will be instructed to record dosing in a dosing diary which will be reviewed at each visit, in combination with drug accountability to confirm treatment compliance. Sites should discuss discrepancies between the diary and the drug log to reconcile actual dosing with the patient at each visit.

4.8 Destruction of Study Drug

For this study, IP (those supplied by BMS or sourced by the investigator) such as partially used study drug containers, vials and syringes may be destroyed on site.

If...	Then...
IP supplied by BMS (including its vendors)	Any unused IP supplied by BMS can only be destroyed after being inspected and reconciled by the responsible Study Monitor unless IP containers must be immediately destroyed as required for safety, or to meet local regulations (eg, cytotoxics or biologics). If IP will be returned, the return will be arranged by the responsible Study Monitor.
IP sourced by site, not supplied by BMS (or its vendors) (examples include IP sourced from the sites stock or commercial supply, or a specialty pharmacy)	It is the investigator's or designee's responsibility to dispose of all containers according to the institutional guidelines and procedures.

It is the investigator's or designee's responsibility to arrange for disposal, provided that procedures for proper disposal have been established according to applicable federal, state, local, and institutional guidelines and procedures, and provided that appropriate records of disposal are kept. The following minimal standards must be met:

- On-site disposal practices must not expose humans to risks from the drug.
- On-site disposal practices and procedures are in agreement with applicable laws and regulations, including any special requirements for controlled or hazardous substances.
- Written procedures for on-site disposal are available and followed. The procedures must be filed with the site's SOPs and a copy provided to BMS upon request.
- Records are maintained that allow for traceability of each container, including the date disposed of, quantity disposed, and identification of the person disposing the containers. The method of disposal, ie, incinerator, licensed sanitary landfill, or licensed waste disposal vendor must be documented.
- Accountability and disposal records are complete, up-to-date, and available for the Monitor to review throughout the clinical trial period.

It is the investigator's or designee's responsibility to arrange for disposal of all empty containers.

If conditions for destruction cannot be met the responsible Study Monitor will make arrangements for return of IP provided by BMS (or its vendors). Destruction of non-IP sourced by the site, not supplied by BMS, is solely the responsibility of the investigator or designee.

Please refer to [Section 9.2.2](#) for guidance on IP records and documentation.

